### 9.2 Determination of Sample Size

Sample size is based on clinical feasibility rather than statistical considerations, accounting for the likely possibility of very few bleeding events, the limited number of available subjects with hemophilia A and pseudotumor, and the need to collect sufficient data to assess safety and efficacy. Approximately 10 subjects will receive study medication (the Treated Population).

### 9.3 Analysis Populations

The Study population is defined as all subjects who provide informed consent. The Treated Population is defined as all subjects who receive study medication. All analyses of efficacy, quality of life and safety will be performed based on the Treated Population.

### 9.4 Demographics and Baseline Characteristics

Demographic and baseline characteristics for all subjects will be summarized using descriptive statistics for continuous variables and frequencies and percentages for categorical variables.

### 9.5 Primary Endpoints

The primary endpoints are:

- The number of breakthrough bleeding events over time requiring the use of alternate hemostatic therapy (bleed rate) related to the pseudotumor
- The number of hospital admissions related to the pseudotumor
- The number of incidences of anemia requiring transfusion or intervention related to the pseudotumor
- The control of progression, stabilization or regression of the pseudotumor (ie, changes in size) as measured by yearly assessments including CT and/or MRI

The study investigator will determine whether the reported event was related to the pseudotumor based on a retrospective review of the medical data (eg, bleed location, patient symptoms, etc).

Efficacy analyses will be performed based on the parameters listed above. As there is no control group or placebo in the study, the on-study data will be compared to that listed in the subject's

medical files prior to study enrollment. The efficacy analyses will exclude data acquired during the 4 loading doses (study visit 2). Analyses will be performed on a per-subject basis and in aggregate. Sub-analyses will be considered based upon the included study population.

Demographic and baseline characteristics for all subjects will be summarized using descriptive statistics for continuous variables and frequencies and percentages for categorical variables.

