### *Efficacy Analyses*

The primary outcome for this study is bleeding events specifically related to the pseudotumor over time; total bleeding events will also be recorded and analyzed. Hemostatic efficacy is defined as the rate of breakthrough bleeding related to the pseudotumor (the number of bleeding episodes while on Hemlibra that require alternative hematinic therapy). Sample size is determined based on clinical feasibility rather than statistical considerations, accounting for the likely possibility of very few bleeding events, the limited number of available subjects with hemophilia A and pseudotumor, and the need to collect sufficient data to assess safety and efficacy.

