## 6.10 Efficacy and Quality of Life Assessments

The primary outcome for this study is bleeding events specifically related to the pseudotumor over time; total bleeding events will also be recorded and analyzed.

All bleeding events will be recorded in the patient diary along with the following:

- The date and time of onset
- The anatomical location and severity
- The agent(s) used to control the bleed, the exact dose(s), the number of doses and the time(s) of administration
- The Study Investigator will determine whether the bleeding event was related to the pseudotumor based on a retrospective review of the clinical data

The efficacy of Hemlibra (emicizumab) will be determined by comparing the incidence of bleeding events and use of alternate hemostatic medication on study to the incidences prior to study enrollment and by changes over time.

The following should also be recorded and transmitted to the IHTC within 7 days of their occurrence:

- The admission of the subject to a hospital or medical facility (described in **Section 6.11.3**)
- Incidences of anemia that require transfusion or intervention
- All surgeries or deaths
- Any other AEs or SAEs noted and recorded by a physician

The efficacy of Hemlibra (emicizumab) will be determined by comparing the incidence of hospitalization and anemia that require transfusion or intervention on study to the incidences prior to study enrollment and by changes over time.

The following should be acquired during study visit 2 (if they were not performed within 1 month of study entry and if they are not considered suitable for study purposes) and at every annual study visit and the study close-out visit:

- Radiology (CT and/or MRI) to observe change in the size of the pseudotumor over time (ie, the progression, stabilization or regression of the pseudotumor)

The efficacy of Hemlibra (emicizumab) will be determined by the change in the size of the pseudotumor over time (ie, the control of progression, stabilization or regression of the pseudotumor).

The following will be used to determine changes in quality of life and activity level:

- Haem-A-QoL and EQ-5D-5L will be completed following screening and at every annual study visit and the study close-out visit

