## **9.8 Interim Analysis**

Interim analyses will be conducted yearly at the discretion of the study investigator if sufficient patients are enrolled. At a minimum, an interim analysis will occur at the mid-point of the study (2-years following the date of informed consent of the first study subject). This will include a detailed review of safety data. Depending on the number of subjects enrolled, an interim review of additional data may also be considered.

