## 10.9 Data Monitoring

The IHTC is responsible for the oversight of subject safety.

Safety data collection will commence when each individual subject signs and dates the informed consent form and initiates study procedures and will continue until the study ends or the subject withdraws from the study, whichever occurs first. All SAEs will be reported to and reviewed by the Study Investigator. One non-study physician from the study site will review all SAEs, deaths or other unexpected events and report to the Study Investigator with recommendations. If a patient dies on study, the case will be evaluated in detail to determine its relatedness to the study drug and to determine if the study warrants stopping in the opinion of the Study Investigator.

Any drug-related SAE (SADR) will be reported through Genentech's reporting system, as will all AEs stipulated in **Section 6.11.3.2j**. The study site will maintain a record of all SAE reports, interpretations and recommendations which will be available for Genentech to review upon request. In addition, if a greater than expected number of breakthrough bleeding events, or the development of thrombosis or thrombotic microangiopathy (TMA) outside of the established associations occurs, treatment of the subject with Hemlibra (emicizumab) may be halted. If an anaphylactic reaction to Hemlibra (emicizumab) occurs, then treatment of that patient may be halted. The Study Investigator may withdraw a patient based upon their clinical discretion and patient safety.

During the course of the trial, the IHTC will review safety data at least at the following time points:

- On the occasion of every SAE, death or other unexpected event. The event will be assessed by a non-study physician from the IHTC who will report their findings to the Study Investigator. Any drug-related SAE (SADR) will also be reported through Genentech's reporting system
- Every 3 months on a subject-by-subject basis by a non-study physician from the IHTC
- Comprehensively by a non-study physician from the IHTC during every interim analysis (minimally at the 2-year midpoint of the study).

A non-study physician from the study site and the Study Investigator will make recommendations, if necessary, for study modification or termination because of concerns over

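### Three of the four primary endpoints depend on an open, retrospective judgement of relatedness to the pseudotumor, with no stated common standard for pre-study and on-study events

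*Combined protocol and SAP*

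**What the plan says.** Section 9.5 lists four primary endpoints, three of which carry a relatedness condition:

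- Treated bleeds: "The number of breakthrough bleeding events over time requiring the use of alternate hemostatic therapy (bleed rate) related to the pseudotumor"
- Admissions to hospital, counted under the same condition
- Anemia that led to transfusion or another intervention, again only when linked to the pseudotumor

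The fourth, change in pseudotumor size on yearly imaging, needs no such call.

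Section 9.5 then says who decides: "The study investigator will determine whether the reported event was related to the pseudotumor based on a retrospective review of the medical data". The guidance is two examples (where the bleed was and what the patient reported) and an open-ended etc. Section 6.10 says the same for diary bleeds: "The Study Investigator will determine whether the bleeding event was related to the pseudotumor based on a retrospective review of the clinical data". Sections 5.6 and 6.10.1 repeat it.

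The study is single-arm and open-label. Section 9.5 compares on-study data with each subject's medical file from before enrollment and leaves the loading period out of efficacy.

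For the pre-study period, Section 6.2 asks for bleeds with location, severity, duration and treatment over 16 weeks to 6 months. For complications over 6 months, it asks for those already linked to the pseudotumor, without saying who made the link.

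The plan also contains comparisons that bear on this point. The synopsis (Efficacy Analyses) and Section 6.10 state that "total bleeding events will also be recorded and analyzed". Section 9.6 makes the rate of unrelated treated bleeds a secondary endpoint. Section 6.10 compares hospitalization and anemia before and on study with no relatedness limit.

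**The concern.** With no control group, the three event-count endpoints are read as a change from the pre-study chart. Each count is the number of events multiplied by the share called related. The first factor is recorded; the second is an opinion formed afterwards by someone who, in an open-label single-arm study with no masking described, can be expected to know which period the event belongs to.

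A difference in that share needs no bad faith, because the two periods supply different information. On-study bleeds come with diary entries on onset, site, severity and treatment, while pre-study events come from whatever the chart holds. Pre-study complications may also arrive already attributed by another clinician, so the two sides of the comparison may rest on different people and different standards.

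The primary objective is directly exposed, because Section 2.1 defines hemostatic efficacy as the rate of pseudotumor-related breakthrough bleeding.

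**Working it through.** The plan has no figure to reproduce. Section 9.2 sets about 10 subjects by feasibility, and Section 9.1 gives descriptive statistics only, with no alpha, power or effect size. The question is how far classification alone can move the result.

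**1. Identity.** Let the total treated-bleed rate be the same in both periods, with share s_pre called related before and s_on called related on study. The total rate cancels:

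apparent rate ratio = s_on / s_pre

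The documents give no shares, so these are assumptions:

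| s_pre | s_on | apparent ratio | reading |
|---|---|---|---|
| 0.60 | 0.60 | 1.00 | no change |
| 0.60 | 0.50 | 0.83 | 17% decrease |
| 0.60 | 0.40 | 0.67 | 33% decrease |
| 0.50 | 0.60 | 1.20 | 20% increase |

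**2. In counts.** From the plan: 10 subjects, a 26-week look-back, 2 years on study less the 4 loading weeks. Assumed: 6 treated bleeds per subject-year in both periods.

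- Pre-study: 10 × 26/52 = 5.0 person-years; 6 × 5.0 = 30.0 bleeds.
- On study: 10 × (2 − 4/52) = 19.2 person-years; 6 × 19.23 = 115.4 bleeds.
- All treated bleeds: 6.0 per year in each period, ratio 1.00.
- Related bleeds at 60% and 50%: 18.0 and 57.7, or 3.6 and 3.0 per year, ratio 0.83.

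**3. Sensitivity with few bleeds.** Assume 2 bleeds per year and a 21-week look-back (midway between 16 and 26). Pre-study bleeds are then about 10 × 21/52 × 2 ≈ 8, of which 60%, or 4.8, are related. Changing the call on 2 of those related bleeds moves the pre-study related rate by 2/4.8 = 42%.

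**4. Chance of a misleading decrease.** The plan specifies no test, so this is only an illustration. It uses Poisson counts, 4,000 runs per scenario and an exact conditional comparison at two-sided 0.05. Look-back was 16 or 26 weeks, follow-up 2 or 4 years less 4 weeks, and total rates 2, 6 or 12 per year. With equal shares, a nominally significant decrease appeared in 1.9% to 3.0% of runs (nominal 2.5%). With 60% before and 50% on study it appeared in 6% to 17%. Only decreases were tallied.

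**5. Effect of the remedy.** If one rule gives the same share in both periods, the ratio returns to 1.00. Counting all treated bleeds also gives 1.00, because the share drops out.

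**The case against.** The strongest reply is that the plan already lets a reader see reclassification. Related plus unrelated treated bleeds make up all treated bleeds, so a stricter on-study call would appear as a matching rise in the unrelated rate, which Section 9.6 compares with the pre-study file. Total bleeds are analyzed as well. With about 10 subjects, listings and per-subject results, a shift would be hard to hide. The plan is descriptive, and the imaging endpoint is untouched.

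Much of this stands, and it limits the point. A reader might infer that admissions and anemia have no attribution-free comparison; Section 6.10 contradicts that, because its comparison of both carries no relatedness limit. A reader might infer that the bias must favor the drug; nothing in the documents fixes its direction. A reader might also take "Interim analyses will be conducted yearly at the discretion of the study investigator if sufficient patients are enrolled" to mean yearly looks at efficacy. Section 9.8 commits the interim to safety review and says only that other data may be considered.

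What does not fall away is that these safeguards help detect a shift after the fact; they do not stop it from entering the primary endpoints. Section 9.5 does not put the all-event results beside them. Nor is anyone assigned to adjudicate endpoints. Section 10.9 describes the non-study physician's role in safety terms: "The event will be assessed by a non-study physician from the IHTC who will report their findings to the Study Investigator". That physician also sees source records (Sections 10.7 and 10.12), so could not readily serve as a reader masked to period.

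**Conclusion.** The point holds as a correctable gap in endpoint definition. Three of the four primary endpoints rest on a retrospective, open-label judgement guided by examples, and the plan does not state that pre-study events meet the same standard.

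The documents show that a classification shift is possible and uncontrolled. They do not show that it will occur, how large it would be or which way it would run. The ratios 0.83 and 1.20 rest on assumed shares; the counts also rest on assumed bleed rates, because the plan gives neither. A reader might conclude that the before/after results are invalid or that the plan hides attribution, but the total-bleed, unrelated-bleed and unrestricted admission and anemia comparisons do not support that. The change should be made, and the study can proceed on its present design with it.

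**What to change.** In Sections 6.10.1 and 9.5:

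1. **Write a rule.** Replace the open judgement with an anatomical criterion based on the baseline CT or MRI. An event is related if its recorded bleed location, bleeding source or admission diagnosis is at the pseudotumor site, including extension shown on later scheduled imaging. Fix the site for each subject by the end of the loading period. Baseline imaging may be acquired during that period, and its data are already excluded from efficacy.
2. **Apply it to both periods and record it.** State that the same rule governs pre-study and on-study events. Record each on-study call when the event is reported and before any efficacy summary, and log later changes. Show results with unclear events counted once as related and once as unrelated, since either default alone could bias the comparison if pre-study charts are thinner.
3. **Show the all-event result alongside.** Beside each related before/after result, present the same comparison for all treated bleeds, all admissions and all qualifying anemia. Use one anemia/transfusion definition for both periods. At present the screening review in Section 7.1 names red-cell transfusion, Section 6.2 asks for any pseudotumor-related anemia, and the on-study endpoint covers transfusion or other intervention.

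The cost is protocol wording, one site record for each of about 10 subjects, a classification log and extra table columns. Imaging and bleed location are already collected, and no treatment decision changes. The downside is that some unrelated events at the same site will be counted, and sparse pre-study charts may leave more unclear events in that period.

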### **1.3 Hemophilic Pseudotumor**

Hemophilic pseudotumor is a rare complication of hemophilia that occurs in 1-2% of patients with severe hemophilia [van Ommeren, Mooren et al. 2000]. It is observed more frequently in geographic areas where hemophilia is diagnosed late, treatment is inconsistently available, prophylaxis is not used due to resource constraints, and in patients who do not recognize that a bleeding event has occurred (eg, moderate or mild deficient patients who experience infrequent bleeds/injuries). Pseudotumors are more commonly observed in adults than pediatric patients [Magallon, Monteagudo et al. 1994] They may be present in patients with hemophilia either with or without an inhibitor and are more common in patients with inhibitors where hemostasis is less well controlled.

A hemophilic pseudotumor consists of an encapsulated progressive cystic swelling of muscle and/or bone caused by recurrent hemorrhage which can cause a serious complication to both life and limb. Pseudotumors have been reported in a wide variety of bones and soft tissues [Liu, White et al. 1988] where repeated and unresolved hematomas lead to encapsulation, calcification and progressive enlargement, with subsequent erosion of adjacent bone. Most commonly the pseudotumor occurs in the pelvis and long bones of lower extremity; they are also observed in muscles, particularly the iliacus, vastus lateralis and soleus. Pseudotumors are best treated early; if left untreated they can result in compression pressure necrosis of adjacent structures, further bleeding, infection, erosion and loss of function and/or life. Complicating early diagnosis is the fact that patients with pseudotumors may be asymptomatic or stable for long periods of time (sometimes decades) before developing complications [Ahlberg 1975, Magallon, Monteagudo et al. 1994, van Ommeren, Mooren et al. 2000].

Hemophilic pseudotumors are most readily diagnosed and monitored using CT or MRI.

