#### 3.1.1 Initial Study Visit (Consent and Screening)

The initial study visit will take place at the IHTC and will comprise subject consent and screening. The subject will be screened per the criteria listed in **Section 4** of this protocol and will include a physical examination and the review/collection of clinical and laboratory data (if not included in the subject's medical records) including:

- Baseline FVIII,\* aPTT, PT and VWF:Ag
- Baseline FVIII inhibitor level
- Baseline CBC w/diff and CMP + direct bilirubin
- Vital signs (blood pressure, pulse, temperature, and respiratory rate) and weight

---

\* If the subject has an inhibitor, then testing for FVIII level may not be medically necessary as FVIII is usually undetectable in such cases. Exceptions exist, such as for a patient who has mild hemophilia with an inhibitor that only recognizes infused FVIII and not endogenous FVIII.

- Serum pregnancy test for female subjects
- Documentation of current or past infection of Hepatitis A, B and C (tests listed below). If documentation is not available, then the tests will be administered as part of the screening process\*
  - HAV:Ab
  - HBV:Ag and Ab (Core and Surface); if HBV:Ag positive, HBV viral load
  - HCV:Ab; if HCV:Ab positive, HCV viral load
- Documentation of HIV infection (if Ab positive, viral load and CD4 count)
- Baseline Haem-A-QoL and EQ-5D-5L
- If an activity monitoring device is standardly utilized by the patient, then permission will be requested to access data for the 1-month period prior to study entry and use of data from the device if continued during the study
- Review of at least 16 weeks, and up to 6 months if available, of data on prior use of hemostatic therapy and number of breakthrough bleeding events
- Review of 6 months of data on prior need for hospitalization or for PRBC transfusion
- Review of therapy prior to study entry with dose and interval and trough level if available on prophylaxis
- Review of history of inhibitor including date of first positive test, highest documented titer and date
- Review of concomitant medications and supplements
- Determination of the date of development or identification of pseudotumor and documentation of radiologic (CT or MRI) scans
- Review of surgeries and procedures

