### 4.2 Inclusion Criteria

Patients must meet the following criteria for study entry:

- Signed informed consent form from the subject, parent or guardian
- Diagnosis of congenital hemophilia A (baseline FVIII level <40%) with or without FVIII inhibitor, either high or low responding, regardless of titer
- Diagnosis of a hemophilic pseudotumor confirmed by radiologic assessment such as CT or MRI
- Any weight or BMI
- Medical documentation of prophylactic or episodic treatment (FVIII or bypassing agent) and the number of bleeding episodes for at least 16 weeks, and up to 6 months if available, prior to entry into the study
- Medical documentation of any need for PRBC transfusion or hospitalization for 6 months prior to entry into the study
- Subjects with a history of an inhibitor should provide documentation of the inhibitor history including date of initial diagnosis of inhibitor, peak titer, and agent utilized for hemostatic control
- Subjects with high titer inhibitors or those with low titer inhibitors who do not respond to FVIII must be willing to use rFVIIa as first line therapy for the treatment of breakthrough bleeding events
- Medical documentation of ITI therapy for subjects with a history of a FVIII inhibitor and ITI, including current FVIII inhibitor titer
- Willingness to discontinue any current prophylactic hemostatic regimen (FVIII or bypassing agent) and/or FVIII ITI therapy for the duration of the study
  - Subjects receiving FVIII prophylaxis must be willing to discontinue their FVIII prophylactic regimen immediately prior to their second loading dose of Hemlibra (emicizumab)
  - Subjects receiving bypassing agent prophylaxis must be willing to discontinue their prophylactic regimen at least 24 hours prior to their first loading dose of Hemlibra (emicizumab)

- Subjects receiving FVIII ITI therapy must be willing to discontinue ITI immediately prior to their first loading dose of Hemlibra (emicizumab)
- Willingness and ability to comply with scheduled visits, treatment plans, laboratory tests, and other study procedures, including the health-related questionnaires, activity tracking, and bleed diaries, using systems provided during the study

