### 7.2.2 Day 0 Procedures

#### 7.2.2.1 *Pre-treatment*

- Measurement of vital signs (blood pressure, pulse, temperature, and respiratory rate) and weight
- Confirmation of eligibility
  - Subject should not have received aPCC or rFVIIa within 24 hours prior to study drug administration
  - Subject should not have an active bleeding event

- Subject should not have any other temporary or permanent exclusionary event (at the discretion of the Study Investigator)
- Subjects who are receiving FVIII ITI therapy must discontinue ITI at this time and ITI must remain discontinued for the duration of the study
- Assessment of concomitant medication and supplements
- Assessment of adverse events
- Banked plasma sample [baseline antidrug antibody levels for Hemlibra (emicizumab)] for testing at the central laboratory
- Other diagnostic procedures as needed and ordered by the Study Investigator and recommended by the standard of care

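### The pre-study comparison window ends at entry and can contain the event that led to diagnosis or referral, so on-study rates can fall without a drug effect

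*Combined protocol and SAP*

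**What the plan says.** The study has one arm and about 10 subjects, a number set by feasibility. For the primary endpoints, section 9.5 says: "As there is no control group or placebo in the study, the on-study data will be compared to that listed in the" records that each person already has from before entry. The only data that section 9.5 leaves out are those from the loading period, which lies on the on-study side. Section 6.10 describes the efficacy contrast as "comparing the incidence of bleeding events and use of alternate hemostatic medication on study to the incidences prior to study enrollment and by changes over" the course of follow-up, and makes the same comparison for hospitalization and anemia.

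The look-back is fixed by the inclusion criteria in section 4.2. For bleeds it is "Medical documentation of prophylactic or episodic treatment (FVIII or bypassing agent) and the number of bleeding episodes for at least 16 weeks", extended to 6 months where records exist. For the other events the requirement is "Medical documentation of any need for PRBC transfusion or hospitalization for 6 months prior to entry into the study". Section 6.2 adds documentation of pseudotumor complications, including anemia, over the same 6 months.

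Entry requires radiologic confirmation of the pseudotumor. No section sets a minimum time since identification, a gap between the look-back and entry, or a rule for the event that led to diagnosis or referral. Section 3.1.1 does collect the timing: "Determination of the date of development or identification of pseudotumor and documentation of radiologic (CT or MRI) scans". Section 1.3 describes the natural history: "patients with pseudotumors may be asymptomatic or stable for long periods of time (sometimes decades) before developing complications".

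**The concern.** If a pseudotumor is silent for years and then bleeds, that bleed may be the reason it is imaged, or the reason the patient is sent to this center. Such an index event falls just before entry, inside the look-back. It is likely to be judged pseudotumor-related, which puts it in the primary endpoint category. On-study follow-up of 2 to 4 years has no counterpart, because it is not anchored to an event. The pre-study rate is then too high for the subject's usual course, and the before/after contrast shows a fall that comes from the timing of entry. This is regression to the mean.

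Bleeds, admissions and anemia are exposed. Pseudotumor size is not, because it is compared with baseline imaging and not with an event window. The before/after contrast is the plan's main evidence on whether the drug reduces these rates. With short windows, about 10 subjects and, as section 9.2 expects, possibly very few bleeds, one or two index events can dominate it.

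**Working it through.** The plan has no figure to reproduce: it gives no event rate, effect size, alpha or power. The check asks how large a false fall could be if the drug did nothing.

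**Inputs from the protocol.** About 10 subjects (9.2); look-back of 16 to 26 weeks for bleeds and 26 weeks for admissions (4.2).

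**Assumed, not in the documents.** The background rate *L* per year, unchanged by treatment, and the number *k* of subjects with one index event in the window.

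**Model A: the index event is extra to the background.** With *PY* pre-study person-years, the expected pre-study rate is *L* + *k*/*PY* and the on-study rate is *L*. The apparent fall is 1 − *L*/(*L* + *k*/*PY*).

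Admissions: *PY* = 10 × 0.5 = 5.

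| Index admissions among 10 | *L* = 0.2 per year | *L* = 1.0 per year |
|---|---|---|
| 1 | 1 − 0.2/0.4 = 50% | 1 − 1.0/1.2 = 17% |
| 2 | 1 − 0.2/0.6 = 67% | 1 − 1.0/1.4 = 29% |
| 5 | 1 − 0.2/1.2 = 83% | 1 − 1.0/2.0 = 50% |

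Bleeds, taking a mean look-back of 21 weeks (midway between 16 and 26): *PY* = 10 × 21/52 ≈ 4.0. Two index bleeds add 2/4.0 = 0.5 per year. The fall is 1 − 1/1.5 = 33% at *L* = 1 and 1 − 2/2.5 = 20% at *L* = 2.

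The shorter the window, the larger the effect. One index event in a single subject adds 52/16 = 3.25 per year to a 16-week baseline and 52/26 = 2.0 per year to a 26-week baseline.

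Under model A, removing the index events returns the expected ratio to 1.

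**Model B: an ordinary background event triggers entry.** Suppose every subject enters because at least one Poisson event fell in a window of *w* years. The expected pre-study rate is *L*/(1 − exp(−*Lw*)). With one event per subject deleted it is [*Lw*/(1 − exp(−*Lw*)) − 1]/*w*. With *w* = 0.5:

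| True *L* per year | Pre-study rate, all events | Apparent change | Pre-study rate, index event deleted | Apparent change |
|---|---|---|---|---|
| 1 | 0.5/0.393/0.5 = 2.54 | 61% fall | (1.271 − 1)/0.5 = 0.54 | 85% rise |
| 2 | 1/0.632/0.5 = 3.16 | 37% fall | (1.582 − 1)/0.5 = 1.16 | 72% rise |

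Under model B, keeping the index events creates a false fall and deleting them creates a false rise. In both models the truth (no change) lies within the range formed by the two versions, counting its ends. That is the reason to show both.

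**The case against.** The strongest reply is that nothing in the protocol says patients enter because of an event. Section 4.2 asks for no recent bleed, transfusion or admission, so long-known, stable pseudotumors qualify. Required treatment records, and quarterly visits described as standard of care, fit patients already under follow-up. Section 1.3 makes detection through a complication plausible; it does not say how patients are found. This stands: the share with an index event is unknown, and five in ten is only the far end of an illustration.

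Three further inferences are tempting and are not supported.

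- A reader might see a second asymmetry in the Day 0 check in 7.2.2.1, "Subject should not have an active bleeding event". It adds little: efficacy data from the loading period are excluded anyway, and 2 to 4 years of follow-up come after it.
- A reader might say that the identification date is ignored. Section 9.1 puts all collected data into tables and listings, so it would appear. What is missing is a planned comparison that uses it.
- A reader might conclude that the net bias favors the drug. This one mechanism does, but on-study bleeds are captured prospectively by diary while pre-study bleeds come from records. Under-recording before entry would work the other way.

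Two defenses are weaker. That the analysis is descriptive is true, but a descriptive before/after figure can still mislead. The on-study changes over time in 6.10 depend less on the look-back, but they do not correct an inflated pre-study rate.

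**Conclusion.** The concern holds as a risk. The look-back ends at entry, no time since identification is required, and no rule deals with events that led to diagnosis or referral. On-study rates of bleeds, admissions and anemia can therefore fall without a drug effect. With one index admission in 5 person-years and an assumed background of 0.2 to 1.0 per year, the apparent fall is 50% to 17%. These sizes rest on assumed rates and an assumed number of index events; the documents give neither.

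The documents do not support saying that rates will fall for this reason, or that the overall comparison is biased toward the drug. Nor do they support resting the efficacy statement only on counts with index events removed. Under model B, where an ordinary event triggers entry, that leaves a pre-study rate of 0.54 against a true 1.0, or 1.16 against 2.0, and so over-corrects.

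**What to change.** 1. On the look-back CRF, add one field to each bleed, transfusion and admission: did it lead to identification of the pseudotumor or to referral for this study?
2. In section 9.5, keep the planned before/after comparison and add a prespecified sensitivity table without flagged events. Present the two results as a range, and claim a reduction only if both show it.
3. In that table, use the identification date already collected to mark subjects whose pseudotumor was identified within the look-back.

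The cost is one CRF field and one table. The source records are already required, and sample size, eligibility, treatment and visits do not change. If no event is flagged, the two versions agree and the question is closed.

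There are two drawbacks. The flag is a retrospective judgment, and the reported reduction may be less favorable. Under model B with every subject flagged, the version without index events would hide a true reduction of up to 1 − 0.54/1.0 = 46% at *L* = 1, or 1 − 1.16/2.0 = 42% at *L* = 2. For that reason it belongs beside the planned comparison and should not replace it.
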